## **Trial Outcome Analyses**

The intention-to-treat principle will be used to test the primary, secondary and tertiary aims comparing study outcomes by transfusion strategy. Two-sided tests will be used with an alpha-level=0.05 for all

aims. No adjustment of the alpha level will be made for the secondary and tertiary analyses. Results will be interpreted based upon the observed findings, their designation as secondary or tertiary outcomes, and in comparison to the primary outcome result.

## Primary Outcome Analysis

The primary endpoint (the composite of all-cause mortality and myocardial infarction (death/MI) by 30 days from randomization) will be compared by assigned transfusion strategy using an unadjusted log-binomial regression model with a fixed effect variable for assigned treatment strategy and a random effect for clinical site and accounting for missing data using multiple imputation to impute missing 30-day outcome data.

$$\text{Ln}(p_{ij}) = \beta_0 + \beta_1 \text{Restrictive}_{ij} + \alpha_i + \epsilon_{ij}$$

where  $p_{ij} = \text{Prob}(\text{Primary Endpoint} = 1 \mid \text{Participant Assigned Treatment and Site})$ ,

$i = \text{site}$ ,  $j = \text{participant}$ ;

$\alpha_i$  is the random intercept for site  $i$

We will present the estimated risk ratio, 95% CI and p-value for the Restrictive Strategy versus the Liberal Strategy based on this model. Markov Chain Monte Carlo (MCMC) multiple imputation methods will be used to impute the missing 30-day outcome values (yes/no) for death and MI based on all available observed data (baseline, in-hospital and 30-day variables). Ten imputed data sets will be created, a log-binomial model with random effects for site will be estimated for each imputed data set, and the results will be pooled to obtain a single estimate of treatment effect with an adjusted standard error. A log-binomial model with random effects for site will be created from patients with non-missing 30-day death/MI data as a sensitivity analysis. Also, if significant imbalances in baseline risk factors are detected between the two randomized treatment groups, a multivariable log-binomial regression model adjusting for the imbalanced factors will be created as a sensitivity analysis. If adherence to the protocol is a concern, a per protocol analysis, including only patients who undergo transfusion according to their assignment (and adjusting for baseline factors that are associated with adherence to the treatment protocol, will be conducted as a sensitivity analysis.

For each of these models, the primary hypothesis test will be a two-sided test with  $\alpha = 0.05$ :

$$H_0: \text{RR} = 1.00 \text{ versus } H_A: \text{RR} \neq 1.00 \text{ using a two-sided alpha-level} = 0.05$$

such that  $\text{RR} = e^\beta$  where  $\beta$  is the coefficient for the Restrictive assigned strategy (versus Liberal assigned strategy) from the log-binomial model for the primary endpoint. If superiority of one of the two transfusion

strategies is not demonstrated through the primary hypothesis test, a second hypothesis test of interest is the non-inferiority of the Restrictive Strategy compared to the Liberal strategy. Setting the non-inferior margin to a 15% relative increase, we will conduct the following one-sided non-inferiority hypothesis test with  $\alpha=0.025$ :

$H_0: RR \geq 1.15$  versus  $H_A: RR < 1.15$  using a one-sided  $\alpha$ -level=0.025.

With this test, rejecting the null hypothesis leads to the conclusion that the restrictive arm is non-inferior to the liberal arm. This is equivalent to the demonstrating that the entire 95% confidence interval for the estimated RR is  $< 1.15$ .

Among all patients with 30-day outcome data, the observed proportion of patients who experience the primary endpoint in each assigned group, the risk ratio (Restrictive versus Liberal) and 95% confidence interval, the risk difference (Restrictive – Liberal) and 95% confidence interval will be calculated and presented. See Table 2. We will determine whether this estimated 95% confidence interval for the RR includes 1.00 to assess superiority and whether it is  $< 1.15$  to assess non-inferiority of the Restrictive strategy. All available data from randomization through 30 days will be used to identify death and MI outcomes; for patients with incomplete follow-up, we assume that no event occurred after the time of last contact.

Kaplan-Meier methods will be used to display the cumulative risk of the primary endpoint over the 30-day post-randomization follow-up period for all randomized patients stratified by assigned treatment group (Figure 3a). For the Kaplan-Meier analyses, follow-up will be censored at the time of withdrawal, lost-to-follow-up, or 30 days, and a log-rank statistic will be used to compare the two curves. The estimated risks at 30-days and the risk difference and 95% confidence interval at 30-days will be presented.

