The mean hemoglobin concentration at 1, 2, and 3 days post-randomization will be compared between the assigned treatment groups with a Student's t-test. Mixed random effect models will be used to describe the daily mean hemoglobin concentrations during the initial hospitalization following randomization and to compare these repeated measures by assigned treatment group. The mean number of red blood cell transfusions in each randomized treatment group will be described, and a simple Poisson test will be used to test whether the number of units of blood differs significantly by assigned transfusion strategy.

4.c Primary Outcome Analysis

The intention-to-treat principle will be used for all randomized transfusion strategy comparisons of study outcomes. A two-sided test will be used with an alpha-level=0.05 for the primary outcome, the composite of all-cause mortality and myocardial infarction (death/MI) by 30 days from randomization. The 30-day event rate for the primary outcome will be compared by assigned transfusion strategy using an unadjusted log-binomial regression model with a fixed effect variable for assigned treatment strategy and a random effect for clinical site. The primary analysis will involve the estimated relative risk and significance level obtained from the model accounting for interim monitoring and missing data. Event rates, the relative risk and the absolute difference will be from the observed data will also be presented, and 95% confidence intervals will be calculated.

If significant imbalances in baseline risk factors are detected between the two randomized treatment groups (p<0.05), multivariable log-binomial regression will be used to adjust for potential confounding factors as a sensitivity analysis. If adherence to the protocol is lower than expected, a per protocol analysis, including only patients who undergo transfusion according to their assignment and adjusting for baseline factors that are associated with adherence to the treatment protocol, will be conducted as a sensitivity analysis.

4.d Analysis of Secondary and Tertiary Outcomes

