## **Trial Transfusion Strategies**

The trial compares a restrictive and a liberal approach to transfusion therapy. The transfusion strategy is followed during the index hospitalization from the time of randomization up to 30-days post-randomization, hospital discharge, or death, whichever comes first.

Restrictive Transfusion Strategy: Patients randomized to the restrictive transfusion strategy may receive a transfusion if the hemoglobin concentration falls below 8 g/dL and are strongly encouraged to receive transfusion if the hemoglobin concentration is below 7 g/dL. Transfusion is also allowed when anginal symptoms are determined by the patient's treating physician to be related to anemia and are not controlled with anti-anginal medications. Enough blood is given to increase the hemoglobin concentration to above 7 to 8 g/dL or to relieve anginal symptoms. A post transfusion hemoglobin measurement is required.

Liberal Transfusion Strategy: Patients randomly allocated to the liberal transfusion strategy receive one unit of packed RBCs following randomization and will receive enough blood to raise the hemoglobin concentration to 10 g/dL or above any time during the index hospitalization that the hemoglobin concentration is detected to be below 10 g/dL. A post transfusion hemoglobin measurement showing a hemoglobin level of at least 10 g/dL must be obtained.

For both strategies, blood is administered one unit at a time followed by a hemoglobin measurement. A patient in either group may be transfused at any time without a hemoglobin level if the patient is actively bleeding (e.g., brisk gastrointestinal bleeding) and the treating physician believes an emergency transfusion is needed. A patient in either group with history of congestive heart failure or low ejection fraction may receive diuretics prior to or after transfusion and transfusion may be delayed until the patient can safely tolerate the additional volume. Patients with end stage renal disease may receive transfusion during dialysis if requested by treating physician. The transfusion protocol is suspended for 24 hours if the patient goes to surgery.

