## **Planned Secondary Analyses**

A number of secondary manuscripts will be undertaken to evaluate the effect of specified subgroup variables on treatment effectiveness in greater depth. These analyses will consider specified trial endpoints and other clinical outcomes that are relevant to the research question. The analyses will also explore confounders and mediators that explain the relationships between the subgroup variable, transfusion treatment strategy, and outcomes.

Multivariable regression models (linear, logistic and Cox regression) will be used to elucidate the roles of demographic and clinical factors as predictors of defined clinical and patient reported outcomes in this patient population. Outcomes of interest include the trial primary endpoint, the three secondary endpoints, congestive heart failure, unstable angina or unscheduled coronary revascularization, infection, health related quality of life as measured by the EuroQol-5D at 30-days, and six-month mortality.

We will also take a personalized medicine approach to characterize patients who benefit from a liberal transfusion strategy and patients who do as well, or better, with a restrictive transfusion strategy, with respect to the primary outcome and a few key secondary endpoints. For a given endpoint, we will use machine learning methods to identify baseline characteristics that lead to better outcomes, and we will use generated effect modifier (GEM) models to create a function of the identified risk factors that interacts with assigned treatment. This function may allow us to predict the treatment strategy with which each patient would benefit based on their individual clinical and demographic profile.

We will employ causal inference principles to assess the impact of various hemoglobin thresholds for transfusion on the primary outcome and 30-day death in the MINT trial. Using the observed trial data, we will emulate a parallel target trial with several different hemoglobin transfusion thresholds (< 10 g/dL, < 9 g/dL, < 8 g/dL and < 7 g/dL). All patients will be followed under each of the four transfusion strategies until the time they no longer adhere to that strategy based on the measured hemoglobin levels and transfusions administered. We will apply contemporary causal inference data analytic approaches aimed at minimizing biases to analyze the effect of treatment received (rather than assigned treatment) to determine the best hemoglobin threshold for this patient population.

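### The conditional per-protocol sensitivity analysis selects on transfusion received after randomization, so a liberal patient who dies before any unit leaves with the event while a comparable restrictive patient stays

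*SAP*

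**What the plan says.** SAP section 6, Primary Outcome Analysis, makes the analysis conditional ("If adherence to the protocol is a concern") and gives no threshold. The set is formed by "a per protocol analysis, including only patients who undergo transfusion according to their assignment", and the only correction is "adjusting for baseline factors that are associated with adherence to the treatment protocol". Protocol F4, 4.c has the same rule: "including only patients who undergo transfusion according to their assignment and adjusting for baseline factors that are associated with adherence to the treatment protocol". The SAP applies a two-sided 0.05 test to each of its primary and sensitivity models, so this analysis yields a formal p-value.

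Neither document defines the per-protocol set further. The nearest guide is how each measures adherence:

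- **Liberal arm.** Patients are to "receive one unit of packed RBCs following randomization" (SAP section 1, Trial Transfusion Strategies). A liberal patient with no transfusion is flagged as a violation in Protocol D3, 3.f and reported under Adherence to Assigned Intervention in SAP section 6.
- **Restrictive arm.** Transfusion is permitted below 8 g/dL but not required. The same two sections count only blood given outside the rule, never blood withheld.

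The primary endpoint, death or MI, is counted from randomization to 30 days.

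**The concern.** Adherence becomes known only after randomization, and it asks different things of the two arms. A liberal patient has to live long enough to receive a unit. A restrictive patient complies from the start by receiving nothing. Since the outcome clock starts at randomization, an early death before a unit is both an event and a reason for exclusion, but in one arm only.

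The planned covariates describe patients at baseline. Exclusion here is caused by the outcome itself, so conditioning on baseline severity does not restore comparability.

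The plan would turn to this analysis when adherence is poor, which is when readers most want a reliable companion to the intention-to-treat estimate. An estimate with bias of unknown size and sign cannot do that job.

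**Working it through.** **Inputs.** From SAP section 4: event rate 16.4%; design rates 18.2% versus 14.6%; 3324 analyzable patients, so 1662 per arm at 1:1; two-sided alpha 0.05. From SAP section 6: non-inferiority margin RR 1.15. The share *x* of liberal patients who have an event and never receive a unit is not in the documents; it is an assumption, shown as a range.

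**The plan's own figure.** A pooled chi-square with 1662 per arm and 18.2% versus 14.6% gives 80.06% power, against 80% stated. The inputs reproduce.

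**Early-death path alone, no true effect.** Removing a fraction *x* of the liberal arm, all with the event, leaves

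liberal risk = (0.164 − x)/(1 − x), and RR = 0.164 / that risk.

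At x = 1%: (0.164 − 0.01)/0.99 = 0.1556, so RR = 0.164/0.1556 = 1.054. The standard error of log RR is √[0.836/(1662 × 0.164) + 0.8444/(1645.4 × 0.1556)] = 0.0798. The normal approximation then gives:

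| x | liberal patients removed | RR | false two-sided rejection | chance of showing RR < 1.15 |
|---|---|---|---|---|
| 0 | 0 | 1.000 | 5.0% | 43% |
| 0.5% | about 8 | 1.026 | 6.2% | 30% |
| 1% | about 17 | 1.054 | 10.2% | 19% |
| 2% | about 33 | 1.116 | 27% | 6% |

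These probabilities ignore the random site effect and the imputation.

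**Does baseline adjustment help?** In a simulation of 400,000 patients with no treatment effect, a standard-normal baseline severity score raised both early death and later events (log-scale slope 0.4, an assumption). The log-link model was fitted with and without that score:

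| target x | all randomized | per-protocol, unadjusted | per-protocol, adjusted |
|---|---|---|---|
| 0.5% | 1.003 | 1.029 | 1.031 |
| 1% | 0.998 | 1.056 | 1.057 |
| 2% | 0.995 | 1.110 | 1.110 |

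Adjustment leaves the bias in place even though the score is the true baseline predictor.

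**The opposing path.** Restrictive patients transfused outside the rule are also removed. If they are 5% of the arm with a 30% event risk (assumed), restrictive risk = (0.164 − 0.05 × 0.30)/0.95 = 0.1568, and RR = 0.1568/0.164 = 0.956. Combined with x = 1%, RR = 0.1568/0.1556 = 1.008. At a 50% event risk the combined RR is 0.941.

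**Wider exclusion in both arms.** With fraction *q* excluded at event risk *r*, arm risk = (0.164 − q·r)/(1 − q):

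| liberal q | restrictive q | r | RR |
|---|---|---|---|
| 10% | 3% | 25% | 1.045 |
| 15% | 3% | 25% | 1.084 |
| 15% | 5% | 30% | 1.120 |
| 5% | 10% | 25% | 0.968 |

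**The case against.** The stakes are limited. This is a conditional sensitivity analysis; SAP section 6, Trial Outcome Analyses, tests every aim by intention to treat, and neither document rests the non-inferiority conclusion on the per-protocol set. That stands. A reader might infer that the flaw threatens the primary result or could manufacture a non-inferiority finding. The documents do not support that: the early-death path pushes RR above 1 and makes non-inferiority harder to show.

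A reader might also infer that unstable, overloaded or bleeding liberal patients are excluded. The text does not establish this. SAP section 1 says that, with a history of heart failure or low ejection fraction, "transfusion may be delayed until the patient can safely tolerate the additional volume". It also permits emergency transfusion in active bleeding in either arm and suspends the protocol for 24 hours around surgery. Such patients may well count as compliant; the plan does not say. Even for early deaths, the adherence summaries are descriptive reports rather than a definition of the per-protocol set. They are still the only adherence criteria the plan offers. A literal reading that also removed untransfused restrictive patients would again select after randomization.

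The upper end of the range is demanding. The liberal arm expects 0.164 × 1662 ≈ 273 events, so x = 2% (about 33) requires 12% of them to fall in patients never transfused. A patient with a nonfatal MI can still receive a unit later and stay in, so the path is chiefly early deaths. At 0.5% the distortion is small.

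Finally, the SAP already plans a causal analysis of treatment received under Planned Secondary Analyses. It compares four hemoglobin thresholds, not the assigned arms, so it shows the method is within reach but does not replace this analysis.

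**Conclusion.** The point holds for this sensitivity analysis and no further. As written, it can move the risk ratio away from 1 when the strategies are equivalent, and the planned adjustment does not correct it. For events before any liberal unit, the RR under no effect is 1.03, 1.05 or 1.12 at 0.5%, 1% or 2% of the arm. Across the wider two-arm exclusion scenarios it runs from 0.97 to 1.12, so no net direction can be claimed.

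This rests on a 16.4% risk in both arms, on assumed exclusion fractions and event risks for which the documents give no figures, and on reading the per-protocol rule through the plan's own adherence measures. The intention-to-treat estimate is untouched. The change is worth making before the analysis is run, because the present version could neither support nor challenge the main result.

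**What to change.** Replace the subset analysis in SAP section 6, Primary Outcome Analysis, with the following:

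1. Keep all randomized patients in their assigned arm and follow each until the first deviation, with deviation defined for both arms.
2. Set and justify an analysis window for the first liberal unit. Count events before that unit within the window in the assigned arm. This is an analysis parameter, not a clinical rule.
3. Classify as adherent the delays, emergency transfusions and surgical suspension that SAP section 1 permits. At present the adherence summary counts any restrictive transfusion without a hemoglobin check, although section 1 allows this in active bleeding.
4. Censor at deviation in both arms and weight by inverse probability of censoring, using baseline data and time-updated data actually collected: hemoglobin, troponin, transfusion timing and recorded events. Report weighted 30-day risks, since the log-binomial model for a complete yes/no outcome does not accommodate censoring.

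This is in line with the threshold analysis already planned, in which "All patients will be followed under each of the four transfusion strategies until the time they no longer adhere to that strategy". Running it whenever non-inferiority is claimed, rather than only when adherence is judged a concern, is optional.

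The cost is revised SAP wording, some extra programming and a wider interval. Residual confounding is possible: Protocol E2 requires hemoglobin only on days 1 to 3 after randomization, and Appendix 2 lists no daily clinical-status item. State this as a limitation.

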## **Analysis of Secondary and Other Outcomes**

All of the secondary outcomes and most of the tertiary outcomes are dichotomous endpoints (i.e. presence/absence of an event during the 30-day study period). The pre-defined secondary outcomes are: 1) all-cause mortality within 30 days; 2) myocardial reinfarction within 30 days; and 3) the composite outcome of all-cause mortality, nonfatal myocardial reinfarction, ischemia driven unscheduled coronary revascularization (percutaneous coronary intervention or coronary artery bypass grafting), or readmission to the hospital for ischemic cardiac diagnosis within 30 days. Other dichotomous outcomes include: 1) all-cause mortality, nonfatal myocardial reinfarction, and unstable angina (i.e. acute coronary syndrome) 2) ischemia driven unscheduled coronary revascularization within 30-days; 3) readmission to the hospital for ischemic cardiac diagnosis, 4) congestive heart failure within 30 days; 5) unscheduled readmission to

hospital for any reason within 30 days; 6) each of the individual cardiovascular outcomes of stroke, pulmonary embolism or deep venous thrombosis, bleeding, and cardiac death within 30 days; 7) each of the individual infectious outcomes of pneumonia and blood stream infections within 30 days.

For each of the dichotomous endpoints listed above, the observed proportion of patients who experience the endpoint in each assigned group, the risk ratio (Restrictive versus Liberal) and 95% confidence interval, the risk difference (Restrictive – Liberal) and 95% confidence intervals will be calculated and presented (Table 2). Superiority of either transfusion strategy for each endpoint will first be evaluated using a two-sided test with  $\alpha=0.05$ . If superiority is not detected, the non-inferiority of the Restrictive strategy will be assessed using a 15% relative non-inferiority margin; that is, the Restrictive strategy will be deemed non-inferior for a given dichotomous endpoint when the entire 95% confidence interval for the estimated RR is  $< 1.15$ . For the 30-day dichotomous outcomes, all available data from randomization through 30 days will be used to identify outcomes. Patients with incomplete follow-up will be assumed to have no event after the time of last contact for these analyses.

The length of hospital stay from randomization to discharge and the number of days in the ICU from randomization to discharge will be described as a mean (sd) or median (first and third quartile) in each assigned group and the difference will be analyzed using non-parametric Wilcoxon rank sum tests (see for example, Table 3). The mean (sd) or median (first and third quartile) will be presented for the EQ-5D utility index value and the EQ-5D Health Today score at 30 days post-randomization, and the difference will be tested based on t-tests or the Wilcoxon rank sum test depending on the distribution of the scores. The proportion of patients who report no problems with each of the 5 individual components of the EQ-5D (Mobility, Self-Care, Usual Activities, Pain/Discomfort, Anxiety/Depression) will be presented stratified by assigned treatment group (Table 3).

The cumulative risk of all-cause mortality through 180-day post-randomization will be estimated using Kaplan-Meier methods for all randomized patients stratified by assigned treatment group (Figure 3b). For the time-to-event analyses, follow-up will be censored at the time of withdrawal, lost-to-follow-up, or 180 days. The estimated risk at 30 days and at 180 days for each treatment group will be presented, and a log-rank statistic will be used to test the hypothesis that the mortality risk over the 180-days is equivalent in the two assigned treatment groups. The estimated risk difference (Restrictive – Liberal) and 95% confidence interval will be presented for cumulative mortality risk at 30 days and at 180 days. If neither strategy is found to be superior based on the log rank test and the 95% confidence interval for the estimated risk difference (RD) at 180-days includes 1.0, the 95% confidence interval for the 180-day mortality risk difference will be assessed using a non-inferiority margin equal to an absolute difference of

3.0%. Thus, if the entire estimated 95% confidence for the 180-day mortality RD is <3.0%, the Restrictive strategy will be considered non-inferior to the Liberal Strategy.

Missing data will not be imputed for the analyses of the secondary and tertiary hypotheses unless critical issues are noted while investigating the missing 30-day primary outcome data.

